	
2. What is the incidence of pregnancy outcomes (including spontaneous abortion, stillbirth, and preterm birth) following receipt of Pfizer-BioNTech bivalent COVID-19 Vaccine during pregnancy compared with no receipt of any COVID-19 vaccine during pregnancy?
 
3. What is the prevalence of birth outcomes (including major congenital malformations and small size for gestational age) in infants born to women who were exposed to Pfizer-BioNTech bivalent COVID-19 Vaccine during pregnancy compared with that in infants born to women who were not exposed to any COVID-19 vaccine during pregnancy?
 
Primary Study Objectives
 
1. To estimate the relative risk of safety events of interest (including myocarditis/pericarditis) in a post-vaccination risk interval, compared with a self-matched post-vaccination control interval, among individuals in the overall population who have received Pfizer-BioNTech bivalent COVID-19 Vaccine.
 
2. To estimate the relative risk of pregnancy outcomes (including spontaneous abortion, stillbirth, and preterm birth) following receipt of Pfizer-BioNTech bivalent COVID-19 Vaccine during pregnancy compared with no receipt of any COVID-19 vaccine during pregnancy.
 
3. To estimate the prevalence odds ratio (POR) of birth outcomes (including major congenital malformations and small size for gestational age) in infants born to women who were exposed to Pfizer-BioNTech bivalent COVID-19 Vaccine during pregnancy compared with that in infants born to women who were not exposed to any COVID-19 vaccine during pregnancy.
 
Secondary Objectives
 
1. To estimate the relative risk of safety events of interest (including myocarditis/pericarditis) in a post-vaccination risk interval, compared with a self-matched post-vaccination control interval, among individuals who have received Pfizer-BioNTech bivalent COVID-19 Vaccine among the following

--	---

PFIZER CONFIDENTIAL

	
subgroups: pregnant women, immunocompromised individuals, individuals with a recorded history of severe COVID-19, and subgroups defined by age (as appropriate for the outcome).
 
2. To estimate the relative risk of pregnancy outcomes (including spontaneous abortion, stillbirth, and preterm birth) following receipt of Pfizer-BioNTech bivalent COVID-19 Vaccine during pregnancy compared with no receipt of any COVID-19 vaccine during pregnancy by subgroups of maternal age.
 
3. To estimate the POR of birth outcomes (including major congenital malformations and small size for gestational age) in infants born to women who were exposed to Pfizer-BioNTech bivalent COVID-19 Vaccine during pregnancy compared with that in infants born to women who were not exposed to any COVID-19 vaccine during pregnancy by subgroups of maternal age.

Country(-ies) of study	United States
Authors	
[name] RTI Health Solutions Waltham, Massachusetts
 
[name] Department of Population Medicine Harvard Medical School & Harvard Pilgrim Health Care Institute Boston, Massachusetts
 
[name], PhD Safety Surveillance Research Pfizer, Inc. New York, New York

090177e19f732934\Approved\Approved On: 14-Dec-2023 13:35 (GMT)

Marketing Authorization Holder(s)

Marketing Authorization Holder(s)	BioNTech Manufacturing GmbH [name]
MAH contact person	[name]
This document contains confidential information belonging to Pfizer. Except as otherwise agreed to in writing, by accepting or reviewing this document, you agree to hold this information in confidence and not copy or disclose it to others (except where required by applicable law) or use it for unauthorized purposes. In the event of any actual or suspected breach of this obligation, Pfizer must be promptly notified.	

090177e19f732934\Approved\Approved On: 14-Dec-2023 13:35 (GMT)

PFIZER CONFIDENTIAL

CT24-WI-GL02-RF02 4.0 Non-Interventional Study Protocol Template For Secondary Data Collection Study

01-Jun-2022

Page 4 of 62

2. LIST OF ABBREVIATIONS

Abbreviation	Definition
CDC	Centers for Disease Control and Prevention
CI	confidence interval
COVID-19	coronavirus disease 2019
EMA	European Medicines Agency
ENCePP	European Network of Centres for Pharmacoepidemiology and Pharmacovigilance
EU	European Union
EUA	emergency use authorization
FDA	Food and Drug Administration
FISMA	Federal Information Security Management Act of 2002
HIV	human immunodeficiency virus
HPHCI	Harvard Pilgrim Health Care Institute
HR	hazard ratio
ICD-10-CM	International Classification of Diseases, 10th Revision, Clinical Modification
ICH	International Council for Harmonisation
ICMJE	International Committee of Medical Journal Editors
IEA	International Epidemiological Association
IEC	independent ethics committee
IRB	institutional review board
IRR	incidence rate ratio
ISPE	International Society for Pharmacoepidemiology
LMP	date of last menstrual period
NBDPN	National Birth Defects Prevention Network
NIST	National Institute of Standards and Technology
PAS	post authorization study
POR	prevalence odds ratio
PPV	positive predictive value
QA	quality assurance

PFIZER CONFIDENTIAL

CT24-WI-GL02-RF02 4.0 Non-Interventional Study Protocol Template For Secondary Data Collection Study

01-Jun-2022

Page 8 of 62

Abbreviation	Definition
QC	quality control
RMP	risk management plan
RP	research partner
RR	risk ratio
RTI	RTI International
SAP	statistical analysis plan
SARS-CoV-2	severe acute respiratory syndrome coronavirus 2
SCDM	Sentinel Common Data Model
SCRI	self-controlled risk interval
STROBE	Strengthening the Reporting of Observational Studies in Epidemiology
TBD	to be determined
TORCH	toxoplasmosis, other [syphilis, varicella-zoster, parvovirus B19], rubella, cytomegalovirus, and herpes
US	United States
VSD	Vaccine Safety Database

090177e19f732934\Approved\Approved On: 14-Dec-2023 13:35 (GMT)

4. ABSTRACT

Title: A Non-Interventional Post-Authorization Safety Study of Pfizer-BioNTech Bivalent COVID-19 Vaccine in the US

Version and date: Version 2.0, 06 December 2023

Main authors: [name], [name], RTI Health Solutions; [name], Department of Population Medicine, Harvard Medical School & Harvard Pilgrim Health Care Institute; and [name], Safety Surveillance Research, Pfizer Inc.

Rationale and background

On 31 August 2022, the United States (US) Food and Drug Administration (FDA) authorized Pfizer-BioNTech bivalent COVID-19 Vaccine (Original and Omicron BA.4/BA.5) for emergency use as a single booster dose for the prevention of COVID-19 in individuals aged 12 years and older (FDA, 2023b). In April 2023, the FDA amended the emergency use authorization (EUA) for Pfizer-BioNTech COVID-19 Vaccine to simplify the vaccination schedule, such that the current bivalent vaccine is to be used for all initial and subsequent doses administered to individuals 6 months of age and older, as follows. Pfizer-BioNTech monovalent COVID-19 Vaccine is no longer authorized for use (FDA, 2023b). As of 11 September 2023, the Pfizer-BioNTech bivalent COVID-19 Vaccine (Original and Omicron BA.4/BA.5) is no longer authorized for use in the US since the updated (2023–2024 Formula) Pfizer-BioNTech COVID-19 Vaccine has become available (Regan et al., 2023). Since the authorization of Pfizer-BioNTech bivalent COVID-19 Vaccine, no signal for myocarditis/pericarditis has been observed in any age group in the Vaccine Safety Database (VSD), with preliminary data suggesting lower rates of myocarditis/pericarditis following booster vaccination with Pfizer-BioNTech bivalent COVID-19 Vaccine as compared with Pfizer-BioNTech monovalent COVID-19 Vaccine among individuals aged 12-39 years (Shimabukuro, 2023). While a potential safety signal for ischemic stroke for individuals aged 65 years and older was initially observed in the VSD, the signal was not subsequently confirmed (Shimabukuro, 2023).

Post-authorization observational studies using real-world data are needed among the general population and among subpopulations of interest (eg, pregnant people, immunocompromised individuals, and the pediatric population) to assess the association between Pfizer-BioNTech bivalent COVID-19 Vaccine and pre-determined safety events of interest, including myocarditis/pericarditis. This protocol describes a proposed observational study of safety events of interest, including myocarditis/pericarditis, occurring in recipients of the Pfizer-BioNTech bivalent COVID-19 Vaccine using claims data and electronic health records data (where available) from data research partners (RPs) participating in the FDA Sentinel System.

The study is a commitment to the US FDA and is also a Risk Management Plan (RMP) Category 3 commitment to the European Medicines Agency (EMA).

PFIZER CONFIDENTIAL

CT24-WI-GL02-RF02 4.0 Non-Interventional Study Protocol Template For Secondary Data Collection Study

01-Jun-2022

Page 11 of 62

Research question and objectives

Research questions

1. What is the incidence of safety events of interest (including myocarditis/pericarditis) following receipt of Pfizer-BioNTech bivalent COVID-19 Vaccine as compared with a self-matched control interval?
2. What is the incidence of pregnancy outcomes (including spontaneous abortion, stillbirth, and preterm birth) following receipt of Pfizer-BioNTech bivalent COVID-19 Vaccine during pregnancy compared with no receipt of any COVID-19 vaccine during pregnancy?
3. What is the prevalence of birth outcomes (including major congenital malformations and small size for gestational age) in infants born to women who were exposed to Pfizer-BioNTech bivalent COVID-19 Vaccine during pregnancy compared with that in infants born to women who were not exposed to any COVID-19 vaccine during pregnancy?

Primary objectives

1. To estimate the relative risk of safety events of interest (including myocarditis/pericarditis) in a post-vaccination risk interval, compared with a self-matched post-vaccination control interval, among individuals in the overall population who have received Pfizer-BioNTech bivalent COVID-19 Vaccine.
2. To estimate the relative risk of pregnancy outcomes (including spontaneous abortion, stillbirth, and preterm birth) following receipt of Pfizer-BioNTech bivalent COVID-19 Vaccine during pregnancy compared with no receipt of any COVID-19 vaccine during pregnancy.
3. To estimate the POR of birth outcomes (including major congenital malformations and small size for gestational age) in infants born to women who were exposed to Pfizer-BioNTech bivalent COVID-19 Vaccine during pregnancy compared with that in infants born to women who were not exposed to any COVID-19 vaccine during pregnancy.

Secondary objectives

1. To estimate the relative risk of safety events of interest (including myocarditis/pericarditis) in a post-vaccination risk interval, compared with a self-matched post-vaccination control interval, among individuals who have received Pfizer-BioNTech bivalent COVID-19 Vaccine for the following subgroups: pregnant women, immunocompromised individuals, individuals with a recorded history of severe COVID-19, and subgroups defined by age (as appropriate for the outcome).

2. To estimate the relative risk of pregnancy outcomes (including spontaneous abortion, stillbirth, and preterm birth) following receipt of Pfizer-BioNTech bivalent COVID-19 Vaccine during pregnancy compared with no receipt of any COVID-19 vaccine during pregnancy by subgroups of maternal age.
3. To estimate the POR of birth outcomes (including major congenital malformations and small size for gestational age) in infants born to women who were exposed to Pfizer-BioNTech bivalent COVID-19 Vaccine during pregnancy compared with that in infants born to women who were not exposed to any COVID-19 vaccine during pregnancy by subgroups of maternal age.

Study design

The study will use a self-controlled risk interval (SCRI) design to assess general safety events (ie, non-pregnancy related safety events of interest, including myocarditis/pericarditis) and a cohort design to assess pregnancy outcomes (spontaneous abortion, stillbirth, and preterm birth) and birth outcomes (major congenital malformations and small size for gestational age). The SCRI study design is appropriate for studying acute events with well-defined risk periods and avoids confounding by time-invariant characteristics (eg, age, sex, pre-existing comorbidities).

To assess the feasibility for planned analyses, a monitoring analysis will be conducted to describe vaccine utilization among the overall population, among immunocompromised individuals, among individuals with a history of severe COVID-19, and in subgroups defined by age as well as among women who may have been exposed during pregnancy.

The study period will start on the date that Pfizer-BioNTech bivalent COVID-19 Vaccine was granted EUA in the US (31 August 2022) and will end a minimum of 2 years after this date.

Population

The source population for this study will be health plan enrollees from data RPs that contribute data from claims and electronic health records to the FDA Sentinel System. The planned data sources for the study are CVS Health, Carelon Research (formerly HealthCore, Inc.), Health Partners, Humana, and Optum Research Database; additional data sources may also be added.

Individuals will be eligible for the analysis of general safety events if they are aged ≥ 6 months during the study period and have continuous medical and pharmacy insurance coverage for at least 12 months before their vaccination date or from birth until the vaccination date (for children aged younger than 12 months on the vaccination date). For children aged younger than 12 months on the vaccination date, a delay in enrollment from birth (duration to be specified in the statistical analysis plan (SAP) may be allowed.

Women will be eligible for inclusion in analyses of pregnancy and birth outcomes if they are aged between 12 and 55 years, had a pregnancy outcome recorded during the study period, and had continuous medical and pharmacy coverage from at least 12 months before the vaccination date until the end of pregnancy. Analyses of major congenital malformations and small size for gestational age will be limited to singleton pregnancies ending in a live birth.

The following subgroups will be identified for descriptive and comparative safety analysis: pregnant women, immunocompromised individuals, individuals with a recorded history of severe COVID-19, and subgroups defined by age (as appropriate for the outcome). Subgroup analysis of pregnancy outcomes and birth outcomes will be conducted by maternal age group.

Variables

Safety events

Safety events of interest will be identified in claims and electronic health records (where available, as not all data RPs will have access to electronic health records) using predefined algorithms based on diagnosis codes, and procedure and/or pharmacy dispensing codes as appropriate.

The following general safety events will be assessed. Unless otherwise noted, all general safety events will be assessed in individuals aged ≥ 6 months.

- Cardiac: myocarditis/pericarditis, acute myocardial infarction
- Neurologic: acute disseminated encephalomyelitis, Bell's palsy, convulsions (in children aged 6 months to 4 years), encephalomyelitis/encephalitis, Guillain-Barré syndrome, transverse myelitis
- Hematologic: deep vein thrombosis, disseminated intravascular coagulation, immune hemolytic anemia, immune thrombocytopenia, pulmonary embolism, thromboembolic events associated with thrombocytopenia, thrombotic thrombocytopenic purpura, venous thromboembolism, hemorrhagic stroke, ischemic stroke
- Respiratory: acute respiratory distress syndrome
- Other system: anaphylaxis, appendicitis, Kawasaki disease (in children aged 6 months to years), multisystem inflammatory syndrome; multisystem inflammatory syndrome in children (in individuals aged < 21 years)

The following pregnancy and birth outcomes will be assessed in pregnant women or their infants:

- Spontaneous abortion (spontaneous pregnancy loss before 20 completed weeks of gestation)

PFIZER CONFIDENTIAL

CT24-WI-GL02-RF02 4.0 Non-Interventional Study Protocol Template For Secondary Data Collection Study

01-Jun-2022

Page 14 of 62

- Stillbirth (fetal deaths at or after 20 completed weeks of gestation)
- Preterm birth (live birth before 37 completed weeks of gestation)
- Major congenital malformations
- Small size for gestational age

Vaccine exposures

Receipt of Pfizer-BioNTech bivalent COVID-19 Vaccine and other COVID-19 vaccines will be identified in claims and/or electronic health records data via pharmacy dispensing and/or procedure codes. In analyses of pregnant women, exposures occurring within 28 days before the estimated pregnancy start or during pregnancy will be considered. Where quality data from existing linkages with immunization registries are available for use in research studies, immunization registry data will also be used to identify receipt of COVID-19 vaccines.

Covariates

Covariates for analysis of general safety events will include demographics, immunocompromising conditions, pregnancy status, history of severe COVID-19, geographic region, whether vaccination with Pfizer-BioNTech COVID-19 bivalent Vaccine was for a primary or booster dose (if feasible), and formulation type of Pfizer-BioNTech COVID-19 Vaccine (ie, bivalent or multivalent vaccine if additional formulations of Pfizer-BioNTech COVID-19 are authorized during the study observation period) and receipt of other vaccines recommended for routine use on the index date.

The same covariates used to assess general safety events will be also use to assess pregnancy and birth outcomes, as appropriate, in addition to the following descriptive and confounding variables: estimated pregnancy start date; gestational age on the index date (for analysis of pregnancy outcomes only); comorbidities in the 12 months before the index date, including history of anaphylaxis, history of vaccine-related allergies, diabetes (type 1 and type 2), hypertension, cardiovascular disease, cerebrovascular diseases, chronic respiratory disease, chronic kidney disease, chronic liver disease, cancer, epilepsy, infections, connective tissue disorders, thyroid disorders, mood disorders, asthma, obesity, healthcare utilization in the 12 months before or on the index date, history of alcohol abuse and smoking, reproductive history, pregnancy complications recorded during the current pregnancy (i.e. multiple pregnancy, gestational diabetes, preeclampsia/eclampsia, and TORCH infections [toxoplasmosis, other {syphilis, varicella-zoster, parvovirus B19}, rubella, cytomegalovirus, and herpes infections]), and teratogenic medications.

Data sources

The study will use data from data RPs that contribute claims and electronic health records to the Sentinel System. The data sources planned for inclusion in this study are CVS Health (Aetna Research Database), Carelon Research (formerly HealthCore), HealthPartners,

PFIZER CONFIDENTIAL

*CT24-WI-GL02-RF02 4.0 Non-Interventional Study Protocol Template For Secondary Data Collection Study
01-Jun-2022*

Page 15 of 62

Humana, and Optum Research Database. The participation of these data sources in the general safety events and/or pregnancy and birth outcome analyses will be confirmed before finalizing the SAP; additional data sources may also be added.

Study size

Because an SCRI design will be used, statistical power for general safety events will depend on the total number of events in the risk and control intervals combined, the ratio of the duration of the risk and control intervals, and the incidence rate ratio (IRR). For example, using a 2-sided $\alpha = 0.05$ level test, with risk and control intervals of equal duration, 80 events provide 86% power to detect an incidence rate ratio equal to or greater than 2.0.

Data analysis

Analyses will initially be conducted separately within the data from each data RP. Data RP-specific results will be returned to the study coordinating center, Harvard Pilgrim Health Care Institute (HPHCI), which will aggregate results across the data RPs for reporting. Pooled analysis of incidence rate ratios, hazard ratios (HRs), and POR estimates from all data RPs will be conducted using privacy-preserving summary-level data sets (eg, risk set-level data sets) or another appropriate method.

General safety events

In each event-specific analytic cohort for general safety events (which will be assessed using an SCRI design), demographics and comorbidities and other key characteristics will be described. For each general safety event, conditional Poisson regression or another appropriate statistical method will be used to obtain incidence rate ratios and 95% confidence intervals (CIs) in the risk interval compared with the control interval.

Pregnancy and birth outcomes

Among pregnant women, the distribution of demographics, comorbidities, and other potential confounders will be reported and compared between the matched exposed and unexposed cohorts. Covariate balance in the matched cohorts after inverse probability of treatment weighting will be assessed using standardized differences or other suitable methods.

Vaccinated pregnant women will be matched to pregnant unexposed comparators in a ratio of at least 1:1 on maternal age, US state (if feasible, or broader geographic region if not feasible), and pregnancy start date (to address confounding by calendar time). Confounding by other variables will be addressed using inverse probability of treatment weighting, based on propensity scores estimated in the matched population.

Measures of incidence or prevalence of pregnancy and birth outcomes with associated 95% CIs will be estimated within the matched exposed and unexposed cohorts. Cox models or Poisson regression will be used to calculate adjusted HRs or incidence rate ratios and 95% CIs for spontaneous abortion, stillbirth, and preterm birth. For small size for gestational

age and major congenital malformations, logistic regression will be used to estimate PORs and 95% CIs.

Sensitivity analyses

A sensitivity analysis may be considered for general safety events if signals are observed in other studies or surveillance systems and the risk intervals are not well characterized. Quantitative bias analysis of comparative risk estimates for myocarditis/pericarditis may be performed using outcome algorithm validation results from Study C4591009 or other published studies, if the algorithm for myocarditis/pericarditis has not been demonstrated to have adequate performance in these other studies.

To address the potential for misclassification of exposure status in the analysis of pregnancy and birth outcomes, a sensitivity analysis may be performed among data RPs that have linkages to high-quality immunization registry data available (if feasible), and quantitative bias analysis addressing exposure misclassification of comparative risk estimates of pregnancy and birth outcomes will be considered. To address the potential for confounding due to comparisons between vaccinated and unvaccinated pregnant women, a sensitivity analysis will be performed. This sensitivity analysis will be conducted among pregnant women with a recorded history of any monovalent COVID-19 vaccination before cohort entry, which may serve as a proxy for these health-seeking behaviors and risk factors for pregnancy and birth outcomes. This analysis will also address the potential for misclassification of unexposed status, as women with a recorded history of monovalent COVID-19 vaccine receipt may have more complete data on bivalent COVID-19 vaccines than those who do not have a recorded history of monovalent COVID-19 vaccine receipt.

Milestones

The anticipated start of data collection is no later than 30 September 2024, and the end of data collection is anticipated to be no later than 31 July 2026. A monitoring report is planned for no later than 31 January 2025, and a final study report is planned for no later than 31 January 2027.

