9. RESEARCH METHODS

9.1. Study design

The study will use a SCRI design to assess general safety events (ie, non-pregnancy related safety events of interest, including myocarditis/pericarditis; see Section 9.3.2.1 for list of specific events) among the general population and specific subpopulations of interest (immunocompromised individuals, pregnant women, and the pediatric population). A cohort design will be used to assess pregnancy and birth outcomes.

For general safety events, the SCRI design (Figure 1) will compare the incidence of safety events of interest in a predefined post-vaccination risk interval with that in a self-matched post-vaccination control interval, among individuals who have received Pfizer-BioNTech bivalent COVID-19 Vaccine. A buffer period (in which incidence will not be assessed) will be incorporated between the risk and control intervals to avoid any carry over effects from the risk interval into the control interval. Control intervals for each outcome will be defined to reflect the baseline risk of the outcome, and buffer and control intervals will take into consideration the duration of the risk interval, potential seasonality of the outcome, and the recommended timing between the initial bivalent vaccine dose and additional COVID-19

[figure not shown]
PFIZER CONFIDENTIAL

CT24-WI-GL02-RF02 4.0 Non-Interventional Study Protocol Template For Secondary Data Collection Study
01-Jun-2022

Page 23 of 62

vaccine doses. Additionally, as an eligibility criterion for each specific safety event of interest, a set period of time prior to the event date (washout period) in which the individual may not have experienced the safety event of interest will be defined to more plausibly identify incident cases.

Figure 1. Self-controlled risk interval design to assess general safety events

[figure not shown]
COVID-19 = coronavirus disease 2019.

This study design is appropriate for studying acute events with well-defined risk periods. A strength of the SCRI design is that it avoids confounding due to time-invariant confounders (including prior history of COVID-19 vaccination, which may be challenging to identify in claims administrative data). Additionally, because the SCRI design only includes vaccinated individuals, it avoids misclassification of unexposed status arising from incomplete capture of COVID-19 vaccination in claims data.

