9.3.2.1. General safety events

General safety events (which will be assessed using a SCRI design) are listed along with their risk interval definitions in [Table 5](#). Event-specific risk intervals have been defined to reflect a period of potentially increased risk following vaccination. Event-specific control intervals will be defined in a pre-specified period (to be specified in the SAP) following the risk interval. Buffer and control intervals for each outcome will be defined to reflect the baseline risk of the outcome and will take into consideration the duration of the risk interval, the potential seasonality of the outcome, and the recommended timing between the initial bivalent vaccine dose and additional COVID-19 vaccine doses.

Table 5. General safety events

Organ system	Safety event of interest	Risk interval (days following vaccination [Day 0])	Ages to be included in analyses ^a
Cardiac	Myocarditis/pericarditis	1-7	Ages ≥ 6 months
	Acute myocardial infarction	1-28	Ages ≥ 6 months
Neurologic	Acute disseminated encephalomyelitis	1-42	Ages ≥ 6 months
	Bell's palsy	1-42	Ages ≥ 6 months
	Convulsions	1-42	6 months through 4 years
	Encephalomyelitis/encephalitis	1-42	Ages ≥ 6 months
	Guillain-Barré syndrome	1-42	Ages ≥ 6 months
	Transverse myelitis	1-42	Ages ≥ 6 months
Hematologic	Deep vein thrombosis	1-28	Ages ≥ 6 months
	Disseminated intravascular coagulation	1-28	Ages ≥ 6 months
	Immune hemolytic anemia	1-42	Ages ≥ 6 months
	Immune thrombocytopenia	1-42	Ages ≥ 6 months
	Pulmonary embolism	1-28	Ages ≥ 6 months
	Thromboembolic events associated with thrombocytopenia	1-28	Ages ≥ 6 months

090177e19f732934\Approved\Approved On: 14-Dec-2023 13:35 (GMT)

PFIZER CONFIDENTIAL

Table 5. General safety events

Organ system	Safety event of interest	Risk interval (days following vaccination [Day 0])	Ages to be included in analyses ^a
	Thrombotic thrombocytopenic purpura	1-28	Ages ≥ 6 months
	Venous thromboembolism	1-28	Ages ≥ 6 months
	Hemorrhagic stroke	1-28	Ages ≥ 6 months
	Ischemic stroke	1-28	Ages ≥ 6 months
Respiratory	Acute respiratory distress syndrome	1-28	Ages ≥ 6 months
Other system	Anaphylaxis	0-1	Ages ≥ 6 months
	Appendicitis	1-42	Ages ≥ 6 months
	Kawasaki disease	1-42	Ages 6 months through 4 years
	Multisystem inflammatory syndrome	1-42	Ages ≥ 6 months
	Multisystem inflammatory syndrome in children	1-42	Ages < 21 years

COVID-19 = coronavirus disease 2019.

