9.7.1. Analysis of general safety events

For analysis of general safety events (which will be assessed using an SCRI design), Pfizer-BioNTech bivalent COVID-19 vaccinees within each outcome-specific analysis set will be described using demographics, comorbidities, and other key characteristics. For each general safety event, conditional Poisson regression or another appropriate statistical method will be used to obtain incidence rate ratios and 95% CIs in the risk interval compared with the control interval.

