9.7.3.3. Confounding

Comparisons between vaccinated and unvaccinated pregnant women may be confounded, as unvaccinated women may differ substantially with respect to health-seeking behaviors and other risk factors for pregnancy and birth outcomes. For pregnancy and birth outcomes, a sensitivity analysis will be performed among pregnant women with a recorded history of monovalent COVID-19 vaccination before cohort entry, which may serve as a proxy for these health-seeking behaviors. This sensitivity analysis will also address potential misclassification of unexposed status, as women with a recorded history of monovalent COVID-19 vaccination may have more complete data on bivalent COVID-19 vaccination.

Confounding by time-invariant characteristics is not a concern in the SCRI design because it is self-controlled.

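### The abstract counts age as time-invariant in the SCRI design, but children age between the risk and control intervals, so any age trend in convulsions or Kawasaki disease shifts the IRR in one direction

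*Protocol*

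**What the plan says.** The abstract, under study design, credits the SCRI with a design that "avoids confounding by time-invariant characteristics (eg, age, sex, pre-existing comorbidities"). The body makes the same point without naming age. Section 9.1 states: "A strength of the SCRI design is that it avoids confounding due to time-invariant confounders", with prior COVID-19 vaccination as its example. Section 9.7.3.3 states: "Confounding by time-invariant characteristics is not a concern in the SCRI design because it is self-controlled".

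Two outcomes in Table 5 (section 9.3.2.1) are confined to young children: "Convulsions 1-42 6 months through 4 years" and "Kawasaki disease 1-42 Ages 6 months through 4 years". On the comparison period, the same section says: "Event-specific control intervals will be defined in a pre-specified period (to be specified in the SAP) following the risk interval". Section 9.1 adds a buffer between the two intervals and gives no length for it.

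On analysis, section 9.7.1 says that "conditional Poisson regression or another appropriate statistical method will be used to obtain incidence rate ratios and 95% CIs in the risk interval"; the reference is the control interval, and no age term is stated. Table 7 uses age only descriptively for general safety events, assessed on the index date. Section 9.9 accepts that the SCRI can be subject to time-varying confounding and plans to reduce it by keeping each person's total observation short. It does not mention age. Sections 9.1 and 9.3.2.1 name seasonality as a consideration in setting the intervals, but not age.

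**The concern.** Age has two parts in a self-controlled comparison. Age at vaccination is fixed for each child and cancels. Attained age is not fixed: every child is older in the control interval than in the risk interval. Because the order of the intervals is the same for everyone, the effect does not average out across children.

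If background incidence falls with age, the control interval has too few events and a vaccine with no effect shows an IRR above 1. If it rises with age, the IRR is pulled below 1 and a real excess can be hidden, which is the more serious error in a safety study. Ageing over a couple of months is negligible in adults, but may not be in a child of 6 or 12 months.

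The protocol itself applies the principle elsewhere. Sections 9.1 and 9.9 prefer a cohort design for outcomes such as spontaneous abortion because their risk changes substantially over time. Listing age as controlled by design invites the author of the SAP to treat the matter as closed.

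**Working it through.** **The plan's own figure.** Table 8 (section 9.5.1) assumes risk and control intervals of equal length and gives 86% power for 80 events at IRR 2.0, two-sided alpha 0.05. With the signed-root likelihood-ratio formula for self-controlled case series and interval share r = 0.5:

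- p = 2/3, A = 2[p ln 2 − ln 1.5] = 0.1133, B = (ln 2)² p(1 − p)/A = 0.943
- power = Φ[(√(80 × 0.1133) − 1.96)/√0.943] = 0.860

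All 24 cells of Table 8 reproduce to within 0.01. The point therefore disputes no stated number; it concerns what the IRR estimates.

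**Inputs from the protocol.** Risk interval 42 days and ages 6 months through 4 years (Table 5); control interval after the risk interval (section 9.3.2.1); a buffer of unstated length (section 9.1).

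**Assumptions.** Control interval of 42 days, as in the equal-length case of Table 8; buffer from 0 days (the lower limit) to 42 days; a log-linear trend in which the background rate is multiplied by f per year of age; no vaccine effect. The protocol gives no age-specific rates, so f is purely illustrative.

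**Gap between midpoints.** Gap = 42/2 + buffer + 42/2, which is 42 days with no buffer and 84 days with a 42-day buffer. A shorter control interval reduces the gap, but the first half of the risk-interval term alone keeps it above 21 days. A 42-day gap is 42/182.6 = 23% of the age lived at 6 months, and 42/(4.99 × 365.25) = 2.3% just before the fifth birthday.

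**Expected IRR with no vaccine effect** = f^(−gap/365.25):

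| Rate multiplier per year of age, f | 42-day gap | 84-day gap |
|---|---|---|
| 0.5 (halves) | 1.083 | 1.173 |
| 0.8 (falls 20%) | 1.026 | 1.053 |
| 0.9 (falls 10%) | 1.012 | 1.025 |
| 1.25 (rises 25%) | 0.975 | 0.950 |
| 2.0 (doubles) | 0.923 | 0.853 |

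Conversely, an upward bias of 5% needs f = 1.05^(−365.25/42) = 0.654, a fall of about 35% per year, at a 42-day gap; at 84 days it needs f = 0.809, a fall of about 19% per year.

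**Effect on false positives.** With equal intervals, SE(ln IRR) = 2/√n for n events. With d = ln(null IRR)/SE, the two-sided rejection rate is Φ(d − 1.96) + Φ(−d − 1.96). Event counts are assumed.

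| Null IRR | 100 events | 1,000 events |
|---|---|---|
| 1.05 | 5.7% | 12.0% |
| 1.083 | 6.8% | 24.3% |
| 1.17 | 12.3% | 69.9% |

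With few events, the bias is small beside the sampling error; it matters for inference when the pooled network supplies many.

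**The case against.** The strongest reply is that the error is one word in a parenthesis of the abstract. Read as age at vaccination, that word is right, and the body sections do not repeat it. Section 9.7.3.3 is true as written, because it speaks only of time-invariant characteristics. Section 9.9 acknowledges time-varying confounding and states a remedy. Section 9.7.1 leaves room for another method, and the interval lengths and model details belong to the SAP. All of this stands, and the absence of an offset term from a protocol would not by itself be a finding. But the remedy in section 9.9 can only shrink the gap, since the control interval is always later and the risk interval is fixed at 42 days, and nothing tells the reader that age is one of the factors meant.

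Several stronger readings are tempting and not supported:

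- *That the IRR will be materially biased.* The protocol gives neither age-specific rates nor a buffer length. Restricting an outcome to young children shows which ages are relevant, not that risk changes over weeks within that range.
- *That the trend could be 10% or more per month of age.* Over the 54 months from 6 months to 5 years, 1.10^54 is about 170-fold. Such a slope cannot describe the whole age range.
- *That a 6-month-old is typical.* Section 7 shows that, before 18 April 2023, bivalent doses in this age group followed at least two monovalent doses, and the authorization ended on 11 September 2023. The youngest infants are the extreme case.
- *That every event in the youngest stratum of section 9.7.4 is affected alike.* Many Table 5 events have risk intervals of days 0-1, 1-7 or 1-28, to which the 42-day illustration does not carry over.
- *That age adjustment was left out because age was thought to be controlled.* No section gives that reason.

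**Conclusion.** The point holds in limited form. The abstract's description of age is wrong for attained age, and for convulsions and Kawasaki disease the stated comparison carries any background age trend into the IRR in a fixed direction. Over trends from a 10% fall per year of age to a halving or doubling, and midpoint gaps of 42 to 84 days, the distortion runs from about 1% to 17%. It is small unless the trend is steep or the gap long. These figures rest on equal 42-day intervals, an assumed buffer and assumed log-linear trends, so they show scale and direction and are not an estimate for this study. Age at vaccination is properly controlled.

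**What to change.** 1. In the abstract, replace *age* with *age at vaccination*, or delete it from the examples.
2. In section 9.9, name attained age as a time-varying factor for outcomes studied in young children.
3. For convulsions and Kawasaki disease, commit to reporting an age-adjusted IRR beside the unadjusted one. One workable method is an offset in the conditional Poisson model, taken from age-specific background incidence among enrolled children in the same research partners, with age bands wide enough to be stable. An offset is preferable to a log-linear age term fitted in the same model: when every child's control interval follows at the same distance, that term is nearly indistinguishable from the vaccine effect.

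The cost is one background-rate query per partner, one model term and some added uncertainty from the estimated offset. The adjusted analysis also brings in between-person rates, which are exposed to the incomplete vaccine capture that the SCRI was partly chosen to avoid. That applies to the adjusted analysis only, and is a reason to keep the unadjusted IRR alongside it.
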